MMC 2015-63 Belladonna and Opium rectal suppository effect on postoperative pain and nausea following Total Laparoscopic and Robot-Assisted Hysterectomy.

01/18/2017

B&O for TLH Post-operative Pain and Nausea Study Protocol

This study is a single-center, double-blind, randomized placebo-controlled trial to assess the impact of immediate postoperative Belladonna and Opium rectal suppository use on postoperative pain and nausea following total laparoscopic and robot-assisted hysterectomy. Study activities to take place at Mercy Medical Center, involving both outpatient and inpatient surgical settings. The duration of the trial will be 12 months, with a goal of enrolling 130 patients during this time period. Patients eligible for trial participation are women between ages 18 and 75 undergoing level I total laparoscopic or robot-assisted hysterectomy with or without bilateral salpingo-oophorectomy, with or without cystoscopy performed post-procedure, with or without lysis of adhesions, and with or without surgical treatment of endometriosis, with no additional surgical procedures being performed (i.e. no lymph node dissection or urogynecologic suspension or sling procedures). Patients will be excluded from the study if they have contraindications to the use of B&O suppositories: these contraindications are glaucoma, severe hepatic or renal disease, bronchial asthma, history of narcotic idiosyncracies, respiratory depression, convulsive disorders, acute alcoholism or delirium tremens, or regular use of an anticholinergic medication (twice per week or more frequently). Patients will be withdrawn from the study if the original planned surgery is not performed. If the original planned study is not performed, a suppository will not be placed following surgery. Patients may also opt to withdraw from the study, or may be withdrawn from the study if there is a failure of the research team to adhere to the study protocol. There will be no financial incentives offered for trial participation.

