A suppository will be placed rectally by a member of the surgical team at the conclusion of surgery, prior to departure from the OR and awakening from anesthesia. Post-operative placement was selected to minimize interaction with intraoperative anesthetic and analgesic medications, to maximize peak plasma concentrations and therapeutic efficacy of Belladonna alkaloids and Opium within the immediate postoperative period, and control for variation in procedure length between study participants. The nurses caring for the patient postoperatively will be blinded to which suppository the patient did receive, but will be made aware that the patient had received a suppository containing either glycerin or one containing belladonna 16.2mg and opium 60mg, equivalent to approximately 6mg of morphine. These nurses will be educated about potential side effects of Belladonna & Opium suppositories, and of potential drug interactions; they will be asked to document and to inform the covering provider of the occurrence of any such adverse effects. Patients remaining in the hospital overnight following their surgery will undergo a postoperative exam by a resident physician familiar with the study protocol and familiar with potential side effects of the B&O suppository; this physician will inquire about and document the presence of any such side effects. Standard of care at Mercy Medical Center is for nurses to assess patient’s postoperative pain by visual analog scale at regular time intervals. Data regarding patients’ visual analog pain scores for the first 12 hours following surgery will be extracted from the electronic medical record and analyzed by the research team. PO and IV narcotic use in IV morphine equivalents, PO and IV NSAIDs, and PO and IV antiemetic use will also be assessed over the first 12 following surgery, this data is to be extracted from the electronic medical record and analyzed by the research team. Study surveillance will not extend beyond the duration of the participant's postoperative hospitalization, usually less than 24 hours.

The costs of the Belladonna & Opium Suppettes and glycerin rectal suppositories used in this study will be covered by University of Maryland Medical Center, Department of Obstetrics, Gynecology and Reproductive Sciences as a supported resident research project. The costs of glycerin suppositories will be covered by Mercy Medical Center Pharmacy.

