We do not anticipate that study participation will result in any uncovered medical costs, as serious side effects from Belladonna and Opium suppositories are estimated at less than 1% occurrence; however, if such adverse medical reactions were to occur, it would be within the postoperative setting and any associated medical costs would be billed to the patient's insurance company as part of the bundled cost of postoperative care.

Due to their historical use, B&O rectal suppositories have not undergone the rigorous Phase I and II clinical trials required of modern pharmaceuticals seeking FDA approval [1], but are available while the FDA makes determinations of efficacy – a regulatory category shared by drugs hydrocodone and morphine [2,3,4]. Common side effects of B&O suppository are related to anticholinergic activity and include dry nose, mouth, throat, skin, and constipation. Serious side effects are estimated at less than 1% occurrence and include orthostatic hypotension, ventricular fibrillation, tachycardia, palpitation, confusion, drowsiness, headache, loss of memory, fatigue, ataxia, CNS depression, rash, antidiuretic hormone release, bloated feeling, nausea, vomiting, biliary tract spasm, dysuria, urinary retention, urinary tract spasm, increased intraocular pain, blurred vision, weakness, respiratory depression, histamine release, physical and psychological dependence, and diaphoresis [5]. Patients enrolled in this trial would be monitored for development of side effects with review to be performed by investigators on a rolling basis.

Scopolamine is an alkaloid with antiemetic properties that is contained within extract of Belladonna. A scopolamine transdermal patch contains 0.6mg of scopolamine alkaloid, and is sometimes used in the pre-operative setting to reduce nausea and emesis in patients reporting a history of motion sickness or of postoperative nausea and vomiting. The recommended dose of scopolamine for use pre-operatively is 0.3 to 0.65mg [6]. Based on the USP Pharmacopeia and gas chromatography data on belladonna extract [7,8], the B&O rectal suppository contains less than 0.02mg of scopolamine, making the total dose of scopolamine received by a patient with a scopolamine patch and a B&O suppository 0.62mg, which is less than the recommended upper limit of dosing for the operative setting. For this reason, patients receiving a pre-operative scopolamine patch will not be excluded from participation in this trial.

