Neither you, nor the patient will be informed which of the two drugs the patient received. Please treat your patient with routine post-operative care, recognizing that they may have already received the equivalent of 6mg of morphine immediately prior to departure from the OR.

Common side effects of B&O suppository are related to anticholinergic activity and include dry nose, mouth, throat, skin, and constipation. Serious side effect are estimated at less than 1% occurrence and include orthostatic hypotension, ventricular fibrillation, tachycardia, palpitation, confusion, drowsiness, headache, loss of memory, fatigue, ataxia, CNS depression, rash, antidiuretic hormone release, bloated feeling, nausea, vomiting, biliary tract spasm, dysuria, urinary retention, urinary tract spasm, increased intraocular pain, blurred vision, weakness, respiratory depression, histamine release, physical and psychological dependence, and diaphoresis. Please notify the GYN resident/fellow if you suspect that your patient is experiencing any of these serious side effects.

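### Active side-effect inquiry is specified only for overnight patients and surveillance ends at discharge, so capture is likely uneven between same-day and overnight patients

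*Combined protocol and SAP*

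**What the plan says.** The opening paragraph describes a trial "involving both outpatient and inpatient surgical settings". It does not give the split.

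The paragraph on suppository placement and postoperative data collection sets out two levels of side-effect capture. For every patient, the blinded postoperative nurses are taught about the drug's side effects and interactions, and "they will be asked to document and to inform the covering provider of the occurrence of any such adverse effects". For some patients there is more: "Patients remaining in the hospital overnight following their surgery will undergo a postoperative exam by a resident physician familiar with the study protocol", and "this physician will inquire about and document the presence of any such side effects". The same paragraph closes the window: "Study surveillance will not extend beyond the duration of the participant's postoperative hospitalization, usually less than 24 hours".

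The side-effect paragraph adds general oversight: "Patients enrolled in this trial would be monitored for development of side effects with review to be performed by investigators on a rolling basis". The Study Participation Alert Form lists both common and serious effects, and its request to nurses reads: "Please notify the GYN resident/fellow if you suspect that your patient is experiencing any of these serious side effects".

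The statistical paragraph names pain, opioid consumption, recovery time and antiemetic rescue when it justifies one-sided tests. It specifies no comparison of side effects between arms.

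**The concern.** How hard anyone looks for side effects, and for how long, depends on whether the patient stays the night. The common effects in the plan are dryness and constipation. A patient usually has to be asked about these, and constipation may appear only after discharge. A nurse who records what she notices will probably record fewer of them than a physician who asks.

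Actual overnight stay is settled after the suppository is placed. Pain and nausea are what the drug is meant to change, and readiness for PACU discharge is itself analysed as an outcome. Randomization balances the planned setting in expectation, but not necessarily the stay that follows treatment. If stay shifts by arm, so does the intensity of capture.

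What is at stake is the side-effect description for a drug that, by the plan's own account, has not been through rigorous early-phase trials. Readers of a placebo-controlled trial will compare side-effect counts by arm whether or not a test is planned. What was not asked before discharge cannot be recovered within the planned surveillance.

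**Working it through.** The plan contains no figure on side-effect capture to reproduce. It gives 65 patients per arm (statistical paragraph) and a rate below 1% for serious effects (side-effect paragraph). It gives no rate for common effects, no overnight share and no detection rate, so these three are assumed below.

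**1. Coverage, side by side**

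| Element | Same-day | Overnight |
|---|---|---|
| Educated, blinded nurse documents effects | Yes | Yes |
| Alert form: notify on suspicion of a serious effect | Yes | Yes |
| Rolling investigator review | Yes | Yes |
| Resident asks about side effects | No | Yes |
| Observation ends | Discharge, same day | Discharge, later |

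The two groups differ in the last two rows. Rolling review can only work on what the other rows have captured.

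**2. Formula**

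Recorded rate = p × [q + (1 − q) × s], where
- p is the rate that would be recorded if every patient were asked,
- q is the share staying overnight,
- s is same-day capture relative to overnight capture.

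**3. Equal stay, equal rates** (p = 30%, q = 0.5, s = 0.5 in both arms)

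0.30 × [0.5 + 0.5 × 0.5] = 0.30 × 0.75 = 22.5% in each arm. A quarter of the events is lost, but no false difference appears.

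**4. Equal stay, a real difference** (p = 30% v 10%, q = 0.5, 65 per arm, two-sided 5% level)

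| s | Recorded | Difference | Power |
|---|---|---|---|
| 1.0 | 30.0% v 10.0% | 20 points | 82% |
| 0.8 | 27.0% v 9.0% | 18 points | 77% |
| 0.5 | 22.5% v 7.5% | 15 points | 67% |
| 0.3 | 19.5% v 6.5% | 13 points | 60% |

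The power column shows the loss of information. The plan specifies no such test.

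**5. Unequal stay, equal rates** (p = 30% in both arms; q = 0.4 on B&O, 0.6 on placebo)

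| s | B&O | Placebo | Ratio |
|---|---|---|---|
| 1.0 | 30.0% | 30.0% | 1.00 |
| 0.8 | 26.4% | 27.6% | 0.96 |
| 0.5 | 21.0% | 24.0% | 0.88 |
| 0.3 | 17.4% | 21.6% | 0.81 |

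Swapping the overnight shares reverses the direction. At s = 0.5 the false difference is 0.03 × 65 = 1.95, about two patients per arm. The standard error of that difference is √[(0.21 × 0.79 + 0.24 × 0.76)/65] = 7.3 points, so a 3-point bias is well under half of it.

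**6. Could the listed serious effects produce such a split?**

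At 1%, each effect touches 0.01 × 65 = 0.65 patients per arm. Drowsiness and urinary retention together give 2 × 0.65 = 1.3. A gap of 60% v 40% is 0.20 × 65 = 13 patients. At the plan's own rates these effects cannot create it. What remains is a change in stay through pain or nausea control, for which the documents give no figure and no sure direction.

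**The case against.** The strongest reply is that nobody goes unobserved. Nurses are educated and asked to document effects in every patient, the alert form lists the effects at the bedside, and investigators review as the trial proceeds. Because the nurses are blinded, this baseline capture should not favour either arm. All of this stands, and it rules out reading the plan as leaving same-day patients unmonitored. It does not close the gap: no duty to ask, schedule or form is stated, and the alert form requests notification only for serious effects, not the common ones.

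A reader might also infer that the planned arm comparison of side effects is biased. The documents do not support that. No such comparison is specified, and a false difference needs overnight stay to differ by arm. Stay may be largely fixed by the planned setting, which randomization balances in expectation. The serious effects most likely to delay discharge are put at under 1%.

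Nor are side-effect notes the only safety-relevant data. Nausea and vomiting are on the side-effect list, and antiemetic use is taken from the record over 12 hours without reference to the overnight exam.

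Finally, the numerical illustrations rest on assumed inputs, and the false differences they show are small beside sampling error. That is correct. They show the mechanism and a range; they do not estimate the bias.

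**Conclusion.** The point holds in a limited form. As written, the plan ties active inquiry and length of observation to length of stay. Mild patient-reported effects are therefore likely under-counted in same-day patients, and under-counting does not require stay to differ between arms. Distortion of a comparison by arm does require it; that is possible in either direction and not established.

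The size is unknown. Under the assumptions shown (30% rate, half staying, same-day capture half as good), a quarter of events would be missed. A 40% v 60% split in stay would produce a false gap of about 1 to 4 points for relative capture between 0.8 and 0.3. If nurses capture as much as the resident does (s = 1), neither effect arises.

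The efficacy outcomes are not affected, since they do not come from the resident's exam. This is a worthwhile, low-cost improvement to safety reporting and does not threaten the trial's main conclusions.

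**What to change.** Have the blinded nurse already caring for each patient complete one short checklist of the side effects listed in the protocol, by asking the patient. Do this at the same pre-set time after suppository placement in everyone, chosen so that same-day patients normally reach it, or at departure if that comes first. Record the time of assessment.

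PACU discharge readiness should not be the anchor, because it is itself an outcome. A general rule of asking before leaving hospital would tie capture to length of stay again.

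Report checklist counts by arm as the common measure. Report overnight resident-exam findings separately, and give the number of same-day and overnight patients in each arm so that readers can see whether stay differed.

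The cost is a short form and brief extra charting by nurses already present, with no added visits or staff. One limitation remains: effects that appear after the checklist time, such as constipation, would still be actively sought only in overnight patients.

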Only the patients of clinical investigators from this trial will be considered for participation in this study. Clinical investigators posting patients for total laparoscopic or robotic hysterectomy at Mercy Medical Center will inform patients of the presence of the clinical trial at the time of surgical posting, using an IRB-approved script (appendix A). The chart number of patients posted for total laparoscopic or robot-assisted hysterectomy will be forwarded to the co-investigator by the clinic surgical coordinator at the time of surgical posting. The co-investigator will review each chart and conduct a telephone interview with each patient prior to surgery to verify trial eligibility and to answer any questions about the trial. Patients will be made aware that study participation is voluntary, and that if they chose to not participate, they will receive standard postoperative pain and nausea pharmacologic management. On the day of surgery, a member of the research team will meet with the patient pre-operatively in a private pre-operative holding area to review and sign a written consent for participation in the trial (Appendix B). This member of the research team would be familiar with the study protocol and risks of the pharmacologic intervention under investigation. These steps will allow patients to be fully informed, and will ensure patient safety and support during the short interval of the study.

On the day of surgery, patients will be randomized to either B&O rectal suppository or to a placebo of glycerin rectal suppository. This study employs a glycerin rectal suppository as a placebo because this over-the-counter medication has limited effects, similar to those of a Belladonna & Opium Suppette, and is similar in size, physical appearance and mechanical properties to a Belladonna & Opium Suppette. A placebo-free comparison group will not be used, as this would change the study design from a double-blind clinical trial to a single-blind clinical trial, with greater potential for investigator bias to influence study results. Additionally,

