The primary hypothesis of the study is that the use of a B&O rectal suppository is associated with decreased postoperative pain and nausea following total laparoscopic or robot-assisted hysterectomy. The visual analog scale (VAS) to be used for assessment of postoperative pain has been demonstrated to be linear in the setting of mild-to-moderate pain [9], such that a 15% decrease in VAS score corresponds to a 15% decrease in subjectively experienced pain. Minimal clinically significant difference in score on the VAS has been shown to occur at approximately 11-14 mm regardless of pain severity [10]. Sample size calculation is based on VAS pain scores following laparoscopic hysterectomy as reported by Ghezzi, et al. [11]. Sample size is set at 65 patients per group (total trial enrollment of 130 patients) with a goal of detecting a 30% decrease in mean VAS score with 80% power, using $p = 0.05$ as a criteria for statistical significance, and accounting for a rate of up to 15% for trial withdrawal, incomplete data, and loss-to-follow-up [12].

For statistical methodology, patient characteristics for the two study arms will be analyzed using a two-sided Student's t-test for continuous variables, or a χ^2 test for categorical variables and proportions. To assess for clinical superiority of the B&O suppository intervention, one-sided Student's t-test (for continuous outcomes) or a one-sided Fisher's Exact test (for categorical outcomes) will be used. One-sided tests are to be used since the addition of B&O is not expected to increase pain, narcotic use, recovery time, or need for rescue anti-emetics a priori. Fisher's Exact test was chosen as a more conservative measure for assessing outcomes, and due to the availability of a one-sided test. A linear regression will be performed on the outcome of PACU discharge readiness time using several different model specifications in order to check for robustness of results.

Bibliography

- [1] CEO of Amerifit Brands, Inc., Nov 7, 2007 Gail T. Costello to Cyrill Siewert.
<http://www.fda.gov/ICECI/EnforcementActions/WarningLetters/2007/ucm076570.htm>.
- [2] Alexander, Thomas J. Lauterio, and Matthew W. Davis Nasr, "Unapproved drugs in the United States and the Food and Drug Administration," *Advances in therapy*, vol. 28, no. 10, pp. 842-856, October 2011.

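### VAS pain sizes the trial, but no pre-operative score is planned and the comparison is unadjusted, so precision available at almost no cost is forgone

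*Combined protocol and SAP*

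**What the plan says.** The document is one combined, unnumbered protocol and analysis plan.

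- **Sizing.** The sample-size paragraph fixes 65 patients per group "with a goal of detecting a 30% decrease in mean VAS score with 80% power", at p = 0.05, allowing up to 15% for withdrawal and incomplete data. The control mean, the SD and the sidedness of the calculation are not stated.
- **Pain data.** The data-collection text describes routine postoperative VAS assessment by nurses and extraction of "visual analog pain scores for the first 12 hours following surgery". No pre-operative score is mentioned anywhere.
- **Analysis.** The statistical methodology paragraph assigns continuous outcomes a one-sided Student's t-test with no covariates. The only regression planned is for PACU discharge readiness time. Patient characteristics are to be compared between arms but are not listed.
- **Population.** Eligible procedures include hysterectomy "with or without surgical treatment of endometriosis". No pain criterion is set.
- **Existing contact.** On the day of surgery "a member of the research team will meet with the patient pre-operatively in a private pre-operative holding area" to complete consent. The randomization envelope is opened later, in the operating room.

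**The concern.** Patients are likely to differ in the pain they bring to surgery and in how they habitually mark the scale, and the eligible population includes women treated for endometriosis. Whatever part of postoperative VAS those differences explain goes into the residual SD of an unadjusted t-test. A score taken before allocation and used as a covariate would remove that part and make the treatment comparison more precise with the same patients. It would also show whether the arms happened to differ in pre-operative pain. As planned, nobody is instructed to collect or use such a score, although a team member is already with each patient at a suitable moment.

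**Working it through.** **Inputs from the protocol:** 65 per group; 15% attrition; 30% decrease in mean VAS; 80% power; p = 0.05; one-sided t-test for continuous outcomes.

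**Assumed:** r, the correlation between pre- and postoperative VAS, from 0 to 0.5.

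**Step 1: the plan's own figure.** It cannot be reproduced forward, because the mean and SD are missing. Working backward, 65 × 0.85 = 55.25, so about 55 evaluable per arm; in the other direction, 55 / 0.85 = 64.7, rounded up to 65. By the normal approximation, the standardized effect detectable with 80% power is

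d = (z for alpha + 0.842) × √(2/55), with √(2/55) = 0.1907.

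- One-sided: (1.645 + 0.842) × 0.1907 = 0.474, so SD / control mean = 0.30 / 0.474 = 0.63.
- Two-sided: (1.960 + 0.842) × 0.1907 = 0.534, so SD / control mean = 0.30 / 0.534 = 0.56.

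Using the t distribution, d is 0.477 and 0.539. The stated 65 is consistent with either sidedness.

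**Step 2: effect of adjustment.** A linear covariate with correlation r leaves a residual SD of SD × √(1 − r²). The expected test statistic, 2.486 one-sided, becomes 2.486 / √(1 − r²), and

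power = Φ(2.486 / √(1 − r²) − 1.645).

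For example, at r = 0.3: 2.486 / 0.954 = 2.607; 2.607 − 1.645 = 0.962; Φ = 83.2%. At r = 0.5: 2.486 / 0.866 = 2.871; 2.871 − 1.645 = 1.226; Φ = 89.0%. The two-sided column replaces 2.486 by 2.802 and 1.645 by 1.960. The last column is 55 / (1 − r²).

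| r | Variance removed (r²) | Power, one-sided | Power, two-sided | Equivalent evaluable n per arm, unadjusted |
|---|---|---|---|---|
| 0.1 | 1% | 80.3% | 80.4% | 55.6 |
| 0.2 | 4% | 81.4% | 81.6% | 57.3 |
| 0.3 | 9% | 83.2% | 83.6% | 60.4 |
| 0.4 | 16% | 85.7% | 86.4% | 65.5 |
| 0.5 | 25% | 89.0% | 89.9% | 73.3 |

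A noncentral t calculation with 107 degrees of freedom agrees to within 0.1 point.

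**Step 3: cost if the covariate is useless.** At r = 0 the model spends one degree of freedom, and random imbalance in the covariate inflates the variance by about 1 + 1/106 on average. One-sided power falls from 80.0% to 79.7%. The table omits this imbalance allowance, which takes about 0.3 points off the one-sided figures; break-even is near r = 0.1.

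**Step 4: chance imbalance.** The standard error of the difference in mean pre-operative score is √(2/55) = 0.19 SD. An imbalance of one standard error shifts the observed postoperative difference by r × 0.19 SD. At r = 0.3 that is 0.057 SD, or 0.057 / 0.477 = 12% of the one-sided design effect. At r = 0.5 it is 0.095 SD, or 20%.

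**The case against.** The strongest case against is that an unadjusted comparison of postoperative pain is a valid randomized analysis and that the benefit of changing it cannot be estimated from these documents. Much of this stands.

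- **A reader might infer that the trial is underpowered.** The documents do not support that. The sizing cites published VAS scores after laparoscopic hysterectomy. If the planning SD was the ordinary between-patient SD of those scores (an assumption, as it is not shown), baseline variation is already in the 65 per group. The calculation above starts from the full 80%.
- **A reader might infer bias.** Allocation is randomized, so a chance imbalance in pre-operative pain is not bias, and the t-test's error rate already allows for it. Step 4 describes random error that adjustment would reduce.
- **A reader might take the endometriosis wording as evidence of a high correlation.** It is one item in a list of permitted procedures, with no proportion and nothing about pain in the holding area. If most women score near zero there, the covariate explains little. Postoperative scores are also recorded under analgesic treatment, which could weaken the correlation further.
- **A reader might infer that pre-operative pain can never be recovered.** The documents are silent on this. The chart, or the unlisted patient characteristics, may contain a score. What can be said is that none is planned for extraction or use.

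The objection does not remove the asymmetry: a loss of about 0.3 power points at worst, against a gain of up to about 9 (one-sided) over the assumed range. A score found in the record afterwards and added to the model would also not be prespecified.

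**Conclusion.** The point holds as a cheap improvement. The gain is negligible at r of 0.1, 1.4 to 1.6 points at 0.2, and exceeds 2 points only from somewhere between 0.2 and 0.3 upward. The upper figures exist only at the top of an assumed range.

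The result assumes about 55 evaluable per arm, 80% power before adjustment, and a linear relation between the two scores. The choice of sidedness hardly matters. The correlation also depends on which postoperative VAS value is analysed, which the protocol does not define. That omission and the missing planning mean and SD are more basic gaps than this one.

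**What to change.** Two changes, which must go together, since the score gains nothing unless the analysis uses it:

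1. **Consent text.** Add one VAS pain mark at the holding-area meeting, recorded before the envelope is opened.
2. **Statistical methodology paragraph.** For postoperative VAS, replace the unadjusted t-test with a prespecified linear model on treatment arm with pre-operative VAS as a linear covariate. State which postoperative VAS value over the 12 hours is the outcome. If a pre-operative score is missing, impute the overall mean of the observed pre-operative scores, both arms together, so that no patient is dropped.

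Cost: under a minute per patient at an existing contact, one more data field and one degree of freedom. No extra visit, staff or patients are needed, and treatment is unchanged.

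### Pre-operative scopolamine patch use is allowed but is neither named as a baseline variable nor used in the antiemetic comparison (minor)

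*Combined protocol and SAP*

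**What the plan says.** The document has no numbered sections, so places are named by their content.

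- **Hypothesis.** Nausea stands beside pain in the primary hypothesis, that "the use of a B&O rectal suppository is associated with decreased postoperative pain and nausea".
- **Scopolamine paragraph of the safety background.** "A scopolamine transdermal patch contains 0.6mg of scopolamine alkaloid", and it is used before surgery "in patients reporting a history of motion sickness or of postoperative nausea and vomiting". For the study drug, "the B&O rectal suppository contains less than 0.02mg of scopolamine". The two are added, "making the total dose of scopolamine received by a patient with a scopolamine patch and a B&O suppository 0.62mg", and because the sum is below the stated upper limit, "patients receiving a pre-operative scopolamine patch will not be excluded from participation in this trial".
- **Eligibility.** The anticholinergic exclusion covers regular use, twice a week or more. It does not remove a patient with a single pre-operative patch.
- **Data extraction.** "PO and IV antiemetic use will also be assessed over the first 12 following surgery". A patch applied before surgery falls outside this by route and by time.
- **Statistical methodology paragraph.** For superiority, a one-sided t-test is planned for continuous outcomes, and "a one-sided Fisher's Exact test (for categorical outcomes) will be used". No stratum or covariate is named. The only regression is for PACU discharge readiness time, and its covariates are not listed. Patient characteristics will be compared by arm, but which ones is not stated.
- **Randomization.** A biostatistician prepares sealed envelopes. No stratification factor is given.

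**The concern.** The protocol itself identifies a concurrent treatment that bears on nausea, says which patients receive it, and admits them. The decision is argued on dose alone; its bearing on the nausea comparison is not discussed.

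Two things are at stake. First, patch use probably predicts the need for rescue antiemetics, through the history that prompts it and through its own action. If the arms differ by chance in the share of wearers, the unadjusted test makes no allowance. Second, the suppository's effect may differ in wearers, since patch and suppository share the one ingredient that the protocol names as antiemetic. Unless patch use is recorded, nobody can look at this afterwards, and a null nausea result would be harder to interpret.

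**Working it through.** **1. The plan's own figure.** Patch 0.6 mg plus suppository at most 0.02 mg gives 0.62 mg, below 0.65 mg. The stated sum reproduces. It addresses safety and says nothing about the analysis.

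**2. Is patch use a legitimate stratification variable?** The patch is pre-operative, and the allocation envelope is opened in the operating room. Patch use is therefore fixed before treatment is revealed, and stratifying on it cannot introduce post-randomization bias.

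**3. How uneven could the arms be?** The evaluable number is 65 × (1 − 0.15) = 55.25, taken as 55 per arm. The share of wearers, f, is not in the documents, so a range is assumed. With allocation unrelated to patch use, the standard deviation (SD) of the between-arm difference in share is √(2f(1 − f)/55). The last column takes an imbalance of 1.96 SD and multiplies it by an assumed 25-point difference in rescue-antiemetic rate between wearers and non-wearers.

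| Assumed f | SD of difference in share | 1.96 SD | Shift in the arm difference |
|---|---|---|---|
| 10% | 5.7 points | 11.2 points | 2.8 points |
| 20% | 7.6 points | 15.0 points | 3.7 points |
| 30% | 8.7 points | 17.1 points | 4.3 points |
| 40% | 9.3 points | 18.3 points | 4.6 points |

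The shift can go either way and averages zero over randomizations.

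**4. What would stratification gain?** The planned one-sided Fisher test was compared with an exact one-sided test stratified by patch use: 55 per arm, alpha 0.05, shares of 10% to 40%, 20,000 simulated trials per setting, all rates assumed. Three examples:

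| Assumed rescue rates, placebo vs B&O | f | Fisher | Stratified |
|---|---|---|---|
| 50% vs 25% in everyone | 20% | 81.6% | 81.8% |
| 50% vs 25% in non-wearers, 25% vs 12.5% in wearers | 40% | 67.7% | 69.4% |
| 40% vs 20% in non-wearers, 60% vs 60% in wearers | 10% | 56.6% | 59.6% |

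Across the six sets of rates tried, the gain was about 0 to 3 points (largest single value 3.6), and stratification did not lose power in any setting.

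**5. What cannot be worked out.** The documents give no share of wearers, no rescue-antiemetic rate, no expected effect on nausea, and no power for nausea; the sample size rests on VAS pain. The actual loss from leaving patch use out therefore cannot be calculated.

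**The case against.** A reader might infer more: that the nausea result is diluted, because wearers carry at least 0.6/0.02 = 30 times the suppository's scopolamine. The documents do not support this.

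- Dilution needs the share of wearers and a smaller effect in them. Neither is given. With assumed rates of 50% vs 25% in non-wearers, and 40% wearers, exact Fisher power falls from 81% to 41% if wearers have the same 50% base rate and no effect, but only to 68% if they have half that base rate and the same relative effect. The answer is set by the assumption.
- The ratio compares content, not effect. The suppository's scopolamine is also under 0.02/0.3 = 6.7% of the lowest recommended dose that the protocol quotes, so if scopolamine were the only route, little effect would be expected in non-wearers either. B&O also contains opium and other alkaloids. It could change nausea by reducing narcotic use, and nausea is itself among its listed side effects.
- Patches go to higher-risk patients, so risk and prophylaxis may offset each other. The direction of the net difference in base rate is unknown.

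A reader might also infer that the patch should count as antiemetic use. It should not: it precedes treatment, and the outcome is rescue need after surgery.

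Other parts of the defence stand. Randomization balances patch use on average, and the unadjusted test remains valid under chance imbalance. Simple randomization cannot be assumed, since the method is not stated. Patch use may turn out to be among the unlisted characteristics compared by arm. Admitting patients on usual prophylaxis is a reasonable pragmatic choice. None of this puts patch use into the antiemetic comparison or guarantees that it will be recorded.

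**Conclusion.** The point holds as a minor one. The plan admits patch wearers, describes them in terms that make patch use a likely prognostic factor, and then neither names it as a baseline variable nor uses it in the antiemetic comparison. The consequence is a chance imbalance left unadjusted and a possible difference in effect that could not be examined. It is not a systematic bias, and dilution has not been shown. The imbalance figures rest on 55 evaluable patients per arm and an assumed wearer share of 10% to 40%; the shift in the arm difference also rests on an assumed 25-point prognostic difference. The power gain rests on assumed rates throughout.

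**What to change.** Leave eligibility unchanged, and do not count the patch as a rescue antiemetic. Then:

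1. Extract pre-operative patch use (yes/no) from the medical record as a baseline variable, and report it by arm.
2. Make the rescue-antiemetic comparison stratified by patch use in all randomized patients: an exact stratified or Mantel-Haenszel test, or a model with arm and patch use.
3. Prespecify the effect in patients without a patch as a supportive estimate only. It should not replace the main comparison: it uses fewer patients and would lose power if the effect is the same in everyone.

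The cost is one more field from a record already being extracted, plus a few lines of analysis-plan text. The return in power is small, and the non-wearer estimate will be less precise than the overall one. The main benefit is that the nausea result can be interpreted with patch use known.
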